### 580 The following tabulations will be made for the AID group:

- Number of participants who stopped AID use and reasons.
  - % time in closed loop and other operational modes.
- Occlusion events that occur while using the AID system.
  - Reportable device malfunctions and other reported device issues.
  - Frequency of use of sleep mode and exploratory outcomes for times with versus without sleep mode.

- 587
- Frequency of use of exercise mode.
- 588 589

## 13. Baseline Descriptive Statistics

Baseline demographic and clinical characteristics of the randomized cohort will be summarized by
 treatment group in a table using summary statistics appropriate to the distribution of each variable.
 Descriptive statistics will include the following:

595	• Age						
596	• Sex						
597	• Race/Ethnicity						
598	Diabetes duration						
599	• Insulin method before enrollment (basal only or multiple daily injections)						
600	CGM use before enrollment						
601	• HbA1c						
602	• BMI						
603	• C-Peptide						
604	GAD Antibody						
605	Total daily insulin						
606	Non-insulin glucose-lowering medications						
607	• SH, DKA, and HHS episodes during the previous 12 months						
608	CHF hospital admissions during the last 12 months						
609	
 
Non-Severe SH episodes during the previous 3 months
 
						
610							
611							
612	14. Planned Interim Analyses						
613							
614	No formal interim efficacy analyses are planned for this study.						
615							
616	The DSMB will review safety data at intervals, with no formal stopping rules other than the guidelines						
017 619	provided in the participant-level and study-level stopping criteria in the Protocol.						
619	The medical monitor will review all cases of severe hypoglycemia and diabetic ketoacidosis irrespective						
620	of device relationship all device related SAEs and all UADEs at the time that they occur during the						
621	study and will review compiled safety data at periodic intervals.						
622							
622							
623	15. Subgroup Analyses						
624							
625	In exploratory analyses, the primary outcome (HbA1c) and time in range 70-180 mg/dL will be						
626	compared in baseline subgroups. Treatment group by subgroup factor interaction terms will be added to						

- 627 the linear models described above.
- 628

Formal tests will be done only if the overall result is statistically significant. Results will be tabulated by 629 subgroups regardless of statistical significance. For continuous variables, results will be displayed in 630 subgroups based on cutpoints although the analysis will utilize the variable as continuous. If there is 631 632 insufficient sample size in a given subgroup, the cutpoints for continuous measures may be adjusted per the observed distribution of values. Cutpoint selection for display purposes will be made masked to the 633 outcome data

634

635	Subgroups	will be a	nalvzed	according t	to the i	following	baseline	factors:
	~ ~ ~ ~ ~ ~ ~ ~ ~							

- Baseline HbA1c 636
- Baseline time in range 70-180 mg/dL 637
- Diabetic medication use 638
- 639 BMI •
  - Total daily insulin (<100 units versus  $\geq$ 100 units)
- 641 • Sex
  - Age (>50 years old versus  $\leq$ 50 years old—assuming sufficient numbers in each category)
  - Race/Ethnicity
- Scores on the Subjective Numeracy Survey 644
- C-peptide level 645
  - Prior medication use (SGLY, GLP1/GIP analog, other)
- Prior CGM and pump use 647
- 648 649

650 651

646

640

642

643

# **16. Multiple Comparison/Multiplicity**

*Hierarchical Analyses* 652

To preserve the overall type 1 error for the primary endpoint and key secondary endpoints as listed in 653 Section 8.2, a hierarchical testing procedure will be used. If the primary analysis for HbA1c results in a 654 statistically significant result (p < 0.05), then testing at the 0.05 level will proceed to the next outcome 655 metric. This process continues iteratively moving to the next variable down on the list until a non-656 significant result is observed, or all 10 variables have been tested. If a non-significant result is 657 658 encountered, then formal statistical hypothesis testing is terminated, and any variables lower on the list will not be formally tested. 659

660

#### All Other Secondary Analyses 661

662 For the other secondary analyses, the false discovery rate will be controlled using the adaptive Benjamini-Hochberg procedure in the following groups: 663

- CGM metrics (continuous and binary) 664 -
- 665 HbA1c metrics (binary)
- Insulin, weight, lipids, creatinine, and blood pressure metrics 666
- **PRO** metrics 667
- Subgroup analyses 668

669	- Meal and exercise challenges
670	- Exploratory analyses
671	
672 673	P-values from safety analyses, sensitivity analyses, and per-protocol analyses will not be adjusted for multiple comparisons.
674 675 676 677 678	17. Exploratory analyses
679	Exploratory Treatment Group Comparisons
680	The following additional treatment group comparisons will be performed:
681 682	- Separate analyses for daytime (6AM to midnight) and nighttime (midnight to 6AM) for the secondary hierarchical CGM outcomes.
683 684 685	
 
Separate sub-analyses for participants negative for GAD antibodies (if GAD antibodies are present in ≥5% of participants) Efficacy (primary and hierarchical) and safety outcomes in participants using an SGLT2 inhibitor.
 

686 687	- Efficacy (primary and hierarchical) and safety outcomes in participants using a GLP-1 receptor agonist.
688 689 690	
 
Efficacy (primary and hierarchical) and safety outcomes in participants with TDI ≥100 units, ≥ 150 units, ≥ 200 units. These may include subgroup analyses – in addition to total daily insulin <100 units versus ≥100 units mentioned above in Section 15.
 

691	
692	Analyses of Complete CGM Data Set
693 694 695 696	CGM metrics will be computed over the entire 13 weeks of the trial (i.e. while including the challenge periods) in the AID group and compared with the baseline CGM metrics using paired t-tests or nonparametric approaches depending on the distribution of the data. Binary outcomes will be assessed using McNemar's test.
697	
698	Plots
699 700 701	Boxplots, scatterplots, and/or cumulative distribution plots will be generated for all primary, hierarchical, and insulin outcomes. Plots will be generated for any other outcomes or analyses where a visual display is considered helpful.

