	This equates with a maximum of 220 using the AID system for 13 weeks and 110 using pre-study basal-bolus insulin delivery method plus the study CGM. Assuming 10% drop out rate in each group, there will be 200 using the system for 13 weeks.
	Approximate Study Goals
	- Minimum 25% MDI users
	- Minimum 30% of a minority race or ethnicity
	- Minimum 10% older than 50 years old
	- Minimum 20% using an SGLT2 inhibitor,20% using a GLP-1 receptor agonist, and a minimum of 10% using both
	Minimum of 15% with TDI> 100 units/day and attempt to enrich cohort with participants with TDI >200 units

PARTICIPANT AREA	DESCRIPTION
	 Minimum of 25% using a form of fixed dosing to calculate meal boluses (e.g., fixed dose at meal or fixed dose for small/medium/large meal [i.e., dose not determined by carbohydrate counting]) Maximum of 60% with HbA1c <8% (based on screening HbA1c or HbA1c available within the last 30 days) and maximum of 10% with screening HbA1c <7%
Treatment Groups	Random assignment 2:1 to an intervention group or control group:
	 Intervention group: t:slim X2 insulin pump with Control-IQ technology and Dexcom G6 CGM
	Control group: Continuation of pre-study basal-bolus insulin delivery method, plus use of study CGM (Dexcom G6)
Participant Duration	~13-17 weeks, depending on duration of run-in phase
Study Duration (planned)	~9 months from first enrollment until last participant visit (assuming 4-month recruitment period; study duration will be extended as needed to complete recruitment)
Protocol Overview/Synopsis	Screening Visit
	• Informed consent obtained and participant screened for eligibility. Testing for eligibility assessment and baseline will include:
	 Medical history, including total daily insulin dose, prior severe hypoglycemia, diabetic ketoacidosis (DKA), hyperosmolar hyperglycemic syndrome (HHS), and hospitalizations for these events.
	 HbA1c with point-of-care device or local lab, unless available from the prior 30 days
	 Focused physical exam, including height and weight to compute body mass index (BMI) and blood pressure
	 Urine pregnancy test for participants capable of becoming pregnant
	o EKG unless performed within 12 months prior to screening
	 Subjective Numeracy Scale Patient-reported outcome (PRO) surveys (see section 8.3), including frequency of non-severe hypoglycemia during the prior 3 months
	CGM Run-in
	Eligible participants will be started on the study CGM, if applicable

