294 295 296 297	For security and confidentiality purposes, participants will be assigned an identifier that will be used instead of their name. Protected health information gathered for this study will be shared with the coordinating center, the Jaeb Center for Health Research in Tampa, FL. De-identified participant information may also be provided to research sites involved in the study.

1298	Chapter 11: Statistical Considerations
1299	11.1 Statistical and Analytical Plans
1300 1301	The approach to sample size and statistical analyses are summarized below. A detailed Statistical Analysis Plan will be written and finalized prior to the completion of the study.
1302 1303 1304	The primary statistical analyses will involve comparisons of the randomized treatment groups. Additionally, certain single-arm analyses will be conducted on the data collected for the AID group as described in section 11.15.
1305	11.2 Statistical Hypotheses
1306 1307 1308	The primary endpoint for this study is HbA1c at 13-weeks adjusted for baseline HbA1c. The intervention will be considered effective if the AID group is superior to the Control group using a statistical significance of α =0.05.
1309	The null/alternative hypotheses for the primary endpoint are:
1310 1311 1312	 Null Hypothesis: There is no difference in mean HbA1c at 13 weeks between AID and Control Alternative Hypothesis: Mean HbA1c at 13 weeks is different for AID and Control.
1313 1314	Similarly, the null and alternative hypotheses for all of the secondary efficacy endpoints in the hierarchy are:
1315 1316 1317	 Null Hypothesis: There is no difference in the endpoint at 13 weeks between AID and Control Alternative Hypothesis: Endpoint at 13 weeks is different for AID and Control.
1318	11.3 Sample Size
1319 1320 1321 1322	The sample size of 330 randomized participants was selected to provide sufficient exposure to the AID system for regulatory purposes. This equates with a maximum of 220 using the AID system for 13 weeks. Assuming 10% drop out rate in each group, there will be 200 using the system for 13 weeks.

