1323 1324 1325 1326 1327 1328	HbA1c data from N=30 participants in the 2IQ pilot study were used to estimate the SD for the power calculation. The SD for baseline values was 1.0%. Assuming a similar SD at follow-up, correlation of 0.3 with baseline, and a two-sided test with type 1 error at 5%, a sample size of N=300 completers will be able to detect an HbA1c difference as small as 0.38% with 90% power. There will be 85% power to detect a difference of 0.35% and 80% power for a difference of 0.33%.
1329	11.4 Efficacy Outcome Measures
1330	11.4.1 Primary Efficacy Endpoint
1331	• HbA1c at 13 weeks (superiority)

1332	11.4.2 Secondary Efficacy Endpoints Included in Hierarchical Analysis
1333 1334	The following secondary endpoints will be tested for superiority, with a hierarchical testing approach to protect the type 1 error rate as described in section 11.13.
1335	• Time in range 70-180 mg/dL
1336	Mean glucose
1337	• Time $> 180 \text{ mg/dL}$
1338	• Time $>$ 250 mg/dL
1339	• CGM-measured prolonged hyperglycemia events (defined in section 11.7.1)
1340	• Time <70 mg/dL
1341	• Time <54 mg/dL
1342	CGM-measured hypoglycemia events (defined in section 11.7.1)
1343	• Coefficient of variation
1344	
1345	11.4.3 Other Secondary Efficacy Endpoints
1346 1347	The following efficacy endpoints are considered exploratory as they are not included in the overall type 1 error rate. All statistical tests are for superiority.
1348	Binary HbA1c Endpoints:
1349	HbA1c <7.0% at 13 weeks
1350	HbA1c <7.0% at 13 weeks in participants with baseline HbA1c >7.5%
1351	HbA1c <7.5% at 13 weeks
1352	HbA1c improvement from baseline to 13 weeks >0.5%
1353	HbA1c improvement from baseline to 13 weeks >1.0%
1354	HbA1c relative improvement from baseline to 13 weeks >10%
1355	HbA1c improvement from baseline to 13 weeks >1.0% or HbA1c <7.0% at 13 weeks
1356	Continuous CGM-Measured Endpoints:
1357	Time in range 70-140 mg/dL
1358	Area over the curve (70 mg/dL)
1359	Low blood glucose index
1360	Time $>$ 300 mg/dL
1361	Area under the curve (180 mg/dL)
1362	High blood glucose index
1363	Binary CGM-Measure Endpoints
1364	Time in range 70-180 mg/dL $>$ 70%
1365	Time in range 70-180 mg/dL improvement from baseline to 13 weeks ≥5%

1366	Time in range 70-180 mg/dL improvement from baseline to 13 weeks \geq 10%
1367	Time $<$ 70 mg/dL $<$ 4%
1368	Time <54 mg/dL $<1\%$
1369	Time in range 70-180 mg/dL $>$ 70% and time $<$ 54 mg/dL $<$ 1%
1370	Other Endpoints (analyzed for superiority as continuous variables):

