# 5. Outcome Measures

- 126127 5.1. Primary Efficacy Endpoint:
  - Superiority in HbA1c at 13 weeks.
- 128 129

130	
131	5.2. Secondary Efficacy Endpoints:
132	
133	
 
Continuous CGM-measured endpoints during 13 weeks of follow-up:
 

134	
 
Time in range 70-180 mg/dL
 

135	$\circ$ Time in range 70-140 mg/dL
136	
 
Mean glucose
 

137	$\circ$ Time >180 mg/dL
138	$\circ$ Time >250 mg/dL
139	
 
CGM-measured prolonged hyperglycemia events (defined in Section 5.3)
 

140	$\circ$ Time <70 mg/dL
141	$\circ$ Time <54 mg/dL
142	• Area over the curve $(70 \text{ mg/dL})$
143	
 
Low blood glucose index
 

144	• CGM-measured hypoglycemia events (defined in Section 5.3)
145	• Coefficient of variation
146	$\circ$ Time >300 mg/dL
147	• Area under the curve $(180 \text{ mg/dL})$
148	
 
High blood glucose index
 

149	
150	• Binary CGM-measure endpoints during 13 weeks of follow-up:
151	• Time in range 70-180 mg/dL $>$ 70%
152	• Time in range 70-180 mg/dL improvement from baseline to 13 weeks $\geq$ 5%
153	• Time in range 70-180 mg/dL improvement from baseline to 13 weeks $\geq 10\%$
154	$\circ  \text{Time} < 70 \text{ mg/dL} < 4\%$
155	$\circ Time < 54 mg/dL < 1\%$
156	• Time in range 70-180 mg/dL $>$ 70% and time $<$ 54 mg/dL $<$ 1%
157	
158	• Binary HbA1c endpoints at 13 weeks:
159	$\circ$ HbA1c <7.0% at 13 weeks
160	• HbA1c $< 7.0\%$ at 13 weeks in participants with baseline HbA1c $> 7.5\%$
161	$\circ$ HbA1c <7.5% at 13 weeks
162	• HbA1c improvement from baseline to 13 weeks $>0.5\%$
163	• HbA1c improvement from baseline to 13 weeks $>1.0\%$
164	• HbA1c relative improvement from baseline to 13 weeks >10%
165	• HbA1c improvement from baseline to 13 weeks $>1.0\%$ or HbA1c $<7.0\%$ at 13 weeks
166	
167	• Insulin delivered during 13 weeks of follow-up:
168	• Total daily insulin (units and units/kg)
169	
 
Total daily bolus (units and units/kg)
 

170	
 
Total daily basal (units and units/kg)
 

171	• Percentage of insulin units delivered as basal.
172	
173	• Weight at 13 weeks:
174	• Weight (kg)
175	
 
Body mass index
 

176						
177	Other Endpoints at 13 weeks:					
178	• Total cholesterol					
179	• HDL cholesterol					
180	• LDL cholesterol					
181	
 
Triglycerides
 
					
182	• Creatinine levels					
183	
 
Blood pressure
 
					
184						
185	• Patient-reported outcome (PRO) measures:					

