### 6. Description of Statistical Methods

- 350 351
- 352 6.1. General Approach:

- All analyses comparing the AID arm with Control arm will follow intention-to-treatment (ITT) 353 • approach, which means participants will be analyzed in the treatment arm assigned by 354 randomization regardless of the actual system use. All randomized participants with any data will 355 be included in the primary analysis and secondary analyses. 356 In the unlikely event that an enrolled participant is later found to be ineligible, the participant 357 • will be excluded from all analyses. 358 • All covariates obtained on a continuous scale will be entered into the models as continuous 359 variables unless it is determined that a variable does not have a linear relationship with the 360 outcome. In such a case, categorization and/or transformation will be explored. 361 All p-values will be two-sided. 362 • Standard residual diagnostics will be performed for all analyses. If values are highly skewed, 363 then a nonparametric or robust regression using M-estimation will be used instead for the 364 primary and secondary outcomes. Previous experience suggests that no transformation, 365 366 nonparametric, or M-estimation analyses will be necessary for HbA1c, mean glucose, % time in range 70-180 mg/dL, or % above 180 mg/dL. Other outcomes like % below 54 mg/dL will likely 367 be skewed with a need for a transformation, nonparametric, or M-estimation. 368 369 370 **6.2 Analysis Cohorts** 371 372 373 Primary and Secondary Analyses: All randomized participants with any data will be included in the primary and secondary analyses. 374 • Any partial data (i.e., missing baseline or follow-up) will be handled using the maximum likelihood 375 method (see Section 7 below). 376 377 • All participants with at least one meal challenge and with the minimum amount of CGM data during these periods – as defined above in Section 5.4 - will be included in the corresponding meal analysis. 378 Similar for participants with at least one scheduled exercise and the exercise analyses. 379 380 381 Per Protocol (PP) Analyses: Per-protocol analyses will be performed for primary outcome and secondary hierarchical outcomes (see 382 Section 8.2 below) only if >5% of participants will be excluded. All of the following criteria must be 383 met for a participant to be included in the per-protocol analyses. The criteria are as follows: 384 385 • 13-week visit completed,
- No major protocol deviations, and

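### McNemar's test is assigned to binary CGM outcomes in the AID-only baseline comparison without excluding the two TIR-improvement endpoints, which have no baseline state (minor, exploratory)

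*SAP*

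**What the plan says.** SAP 17, under Analyses of Complete CGM Data Set, sets up a before/after analysis without a control group: "CGM metrics will be computed over the entire 13 weeks of the trial (i.e. while including the challenge periods) in the AID group". The results are compared with baseline, by paired methods for continuous metrics. For the rest it says: "Binary outcomes will be assessed using McNemar's test". Protocol 11.15.2 gives the same rule.

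The binary CGM endpoints are listed in SAP 5.2 and Protocol 11.4.3. There are six:

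- Four are states that can be read off at either time: TIR above 70%, time below 70 mg/dL under 4%, time below 54 mg/dL under 1%, and the composite of TIR above 70% with time below 54 mg/dL under 1%.
- Two are changes. The SAP words them as "Time in range 70-180 mg/dL improvement from baseline to 13 weeks", with thresholds of 5% and 10%. The Protocol has the same pair, the first being "Time in range 70-180 mg/dL improvement from baseline to 13 weeks ≥5"%.

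Neither document excludes these two from the McNemar rule, defines a baseline state for them, or names another within-group method. SAP 6.1 adds: "All p-values will be two-sided". SAP 16 lists exploratory analyses as one of the groups in which the false discovery rate is controlled by the adaptive Benjamini-Hochberg procedure.

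**The concern.** McNemar's test asks whether participants who switch from no to yes outnumber those who switch from yes to no. For improvement since baseline, the change at baseline is zero, so every participant is a no at the start. Nobody can switch from yes to no. Participants whose TIR falls by 5 or 10 points count the same as those who do not change.

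The statistic then only counts improvers, and its null hypothesis is in effect that nobody improves by the threshold. Ordinary variation between a 14-day baseline and a 13-week follow-up is enough to break that. A small p-value would read as evidence that the device raised TIR when it shows only that TIR varies. The Protocol Summary says the analyses are being prepared for a 510(k) submission, so a p-value of this kind could be quoted.

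**Working it through.** **Figures stated in the plan.** The documents give no figure for the McNemar analysis. The AID completer count is close: 220 × 0.9 = 198, against 200 stated (SAP 4). The primary-endpoint power also reproduces. With residual SD 1.0 × √(1 − 0.3²) = 0.954 and 200 v 100 completers, the standard error is 0.954 × √(1/200 + 1/100) = 0.117. Differences of 0.38, 0.35 and 0.33 then have power of 90%, 85% and 81%, against 90%, 85% and 80% stated.

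**When the test rejects.** Let b be the number improving by the threshold. Discordant pairs the other way number 0, so the exact two-sided p-value is 2 × 0.5^b.

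- b = 5: p = 0.0625
- b = 6: p = 0.031

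Six improvers out of 200 (3%) suffice at the two-sided 0.05 level. The documents state that level for the primary endpoint; it is assumed here.

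**How often that happens with no true change.** Take within-person TIR change as normal with mean 0 and standard deviation SD, and read 5% and 10% as percentage points. Then q = 1 − Φ(threshold/SD), b ~ Binomial(200, q), and the rejection rate is P(b ≥ 6).

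| SD of change (points) | q, 5-point | Rejects, 5-point | q, 10-point | Rejects, 10-point |
|---|---|---|---|---|
| 2 | 0.006 | 0.2% | about 0 | about 0% |
| 2.5 | 0.023 | 30% | about 0 | about 0% |
| 3 | 0.048 | 92% | 0.0004 | about 0% |
| 4 | 0.106 | about 100% | 0.006 | 0.2% |
| 5 | 0.159 | about 100% | 0.023 | 30% |
| 6 | 0.202 | about 100% | 0.048 | 92% |
| 8 | 0.266 | about 100% | 0.106 | about 100% |

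Using 198 in place of 200 changes little (91% at SD 3 for the 5-point test). The rule can also reject when TIR worsens. With a true mean fall of 3 points and SD 5, q = 1 − Φ(8/5) = 0.055, and the 5-point test is significant in about 96% of trials.

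**Which SDs are plausible.** The documents give no SD of within-person TIR change. Protocol 1.3 gives interquartile ranges of 69–82% and 63–83% for TIR in two real-world groups. Dividing the widths by 1.349 gives between-person SDs of 13/1.349 = 9.6 and 20/1.349 = 14.8. With equal variance at both times, the SD of change is SD × √(2(1 − r)).

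- r from 0.3 to 0.9 (assumed): 4.3 to 17.5 points over the two spreads.
- r = 0.95 with the smaller spread: 3.0 points.
- An SD as low as 2.5 needs r of about 0.97 with the smaller spread.

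**Tests that do have a valid null.** In simulations with no true change (198 participants, 10,000 trials per setting), exact McNemar on TIR above 70% rejected in 2.9–3.4% of trials. An exact test of improved by at least 5 points against worsened by at least 5 points rejected in 3.1–3.8%.

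**The case against.** The strongest reply is about reading. The McNemar sentence does not say that it covers every binary endpoint and does not cite the SAP 5.2 list. It follows a sentence about comparing metrics with their baseline values, so it could be taken to mean only outcomes that have one. The coding of everyone as not improved at baseline is inferred, not written. A programmer who declined it would find that the test cannot be formed and would stop. This has force: the defect may be a missing clause rather than a false-positive test waiting to run. But Protocol 11.7.2, headed Binary Outcomes, covers the binary CGM outcomes as a whole, and nothing takes these two out. The sentence fails for them on either reading.

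A reader might go further and infer that both tests will be significant whatever the device does. The documents do not support that. The SD is not given, and the 10-point test is rarely significant at an SD of 4 and reaches 92% only at 6.

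A reader might also infer serious damage to the exploratory false-discovery family. With 10 to 30 independent true-null tests, two spurious rejections raise the chance of a further false one from about 5% to 11–13% under standard Benjamini-Hochberg. But the SAP specifies an adaptive version and does not give the family size, and these tests overlap heavily. In simulations the figure falls to about 8–10% at correlation 0.5 and 3–6% at 0.8. It is a secondary effect of uncertain size.

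Finally, other TIR analyses are sound: second place in the hierarchy (SAP 8.2), the treatment-group comparison of these same endpoints (SAP 8.5), and the paired analysis of continuous TIR in SAP 17. This stands and limits the severity.

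**Conclusion.** The point holds, as a minor one. The McNemar rule is unsuitable for two of the six binary CGM endpoints and suitable for the other four. Under the only coding that lets the test run, the 5-point version is close to certain to be significant with no device effect once the SD of TIR change is above about 3 points; the 10-point version needs about 6.

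This rests on three assumptions: the SD of change, the baseline coding, and 5% and 10% meaning percentage points. The SDs implied by the Protocol's TIR spreads make the 5-point result fairly secure and leave the 10-point result open. The primary analysis, the hierarchical tests and the SAP 8.5 comparison are not affected.

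**What to change.** In SAP 17 and Protocol 11.15.2:

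- Limit McNemar's test to binary outcomes defined at both baseline and follow-up: TIR above 70%, time below 70 mg/dL under 4%, time below 54 mg/dL under 1%, and the composite.
- For TIR improvement of at least 5% and at least 10%, report the percentage improving and the percentage worsening by the same amount, each with a 95% confidence interval. Give no within-group McNemar p-value and keep both out of the exploratory false-discovery family.
- State that inference on these two endpoints comes from the treatment-group comparison in SAP 8.5.

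If a within-group test is wanted, improved against worsened by the same amount holds its level.

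The cost is a short wording change in both documents and the loss of two p-values that carry no information about the device. No new data are needed.
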